3.1.3. Fixed Duration Cohort

Approximately 125 subjects without del17p will be enrolled into this cohort sequentially after the MRD cohort. Subjects will receive 15 cycles of therapy consisting of single-agent ibrutinib for 3 cycles followed by ibrutinib + venetoclax combination treatment for 12 cycles. If emerging data from this study indicate, the duration of combined ibrutinib + venetoclax treatment may be modified to ensure appropriate risk-benefit is maintained, compared to historical controls and other emerging data.

All subjects will be assessed for MRD status in peripheral blood (PB) every 3-12 cycles starting after completion of 6 cycles (C7D1), and in bone marrow (BM) aspirate after completion of 9 cycles (C10D1) and 3 months after completion of the fixed duration Cycle 15 (ie, C19), or earlier if BM is indicated for confirmation of CR per IWCLL response criteria. MRD assessments will be performed using flow cytometry with a sensitivity (lower limit of detection) of 1 CLL cell in 10,000 leukocytes (10^{-4}).

Reintroduction of therapy

[figure not shown]
Subjects with confirmed progression per IWCLL criteria after completion of the fixed duration regimen can be retreated with continuous single agent ibrutinib until disease progression or unacceptable toxicity because it is an established standard of care for treatment of relapsed CLL. For subjects that experience durable efficacy after I+V (ie, time to progression after fixed duration regimen is completed of >2 years), the I+V fixed duration treatment regimen may be repeated based on Investigator's clinical discretion and Medical Monitor's approval. Retreatment is for 15 cycles, until PD or unacceptable toxicity, whichever is earlier.

Subjects will be followed for progression, overall survival (OS), and use of subsequent anticancer agents until study closure.

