### **FD Cohort**

The primary hypothesis of this cohort is that: Complete response rate (CRR) is  $> 37\%$  after 12-cycle Ibr + Ven treatment.

The statistical hypotheses are as follows:

$$H_0: \text{CRR} \leq 37\%$$

versus

$$H_1: \text{CRR} > 37\%$$

These hypotheses will be tested at 1-sided  $\alpha$  level of 0.025 using asymptotic test for the binomial proportion. Since the assumption for sample size and power of this cohort is based on the historical data of subjects without del 17p, the formal hypothesis testing will be performed on the non-del 17p population (section 2).

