## FD Cohort

In the FD cohort, assuming the complete response rate for Ibr + Ven is 50%, 125 subjects without del 17p will provide 83% power to ensure the rate is > 37% at 1-side alpha 0.025. A CR rate of 50% would represent meaningful improvement compared to the CR rate seen with the fixed duration combination of bendamustine + rituximab (31%), and would be an improvement over the CR rate seen with the standard of care fixed duration regimen fludarabine, cyclophosphamide and rituximab (40%) which were obtained in the CLL10 study, which included only patients without del 17p (Eichhorst 2016).

The sample size and power calculations were calculated using the software package, East (Cytel Software Corp, Cambridge, MA) version 6.3.

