### 1.5. Planned Analysis

#### 1.5.1. Interim Analysis

No interim analysis was planned or performed for the randomization period of the MRD cohort or for the FD cohort. The protocol prespecified analyses for pre-randomization phase of MRD cohort were completed as follows:

The safety of Ibr + Ven regimen was assessed in safety run-in subjects (the first 14 enrolled MRD cohort subjects) by Data Review Committee (DRC) consisting of the Medical Monitor or designee, a Drug Safety representative, a biostatistician, and at least 2 participating Investigators. DRC meetings were held first on 01May2017 and then on 07Nov2017 when the 6th and the last (i.e. the 14th) safety run-in subjects, respectively, completed the dose limiting toxicity (DLT) evaluation period (defined as the 5-week venetoclax dose ramp-up in combination with ibrutinib plus an additional week of follow up) respectively. No DLT or TLS occurred in safety run-in subjects. The DRC recommended for the study treatment regimen to move forward without modification in both meetings.

To ensure adequate sample size in the MRD-negative randomization, an early assessment of the MRD negativity rate with Ibr + Ven was performed when the first 30 subjects completed 9 cycles of treatment (6 cycles Ibr + Ven) as of the 30Mar2018 data extraction. MRD negativity in PB was achieved in 23 subjects, rate 77% (95% exact binomial confidence interval [CI]: 58% - 90%). The first 14 subjects also completed MRD testing in both PB and BM at cycle 16 as needed to assess for confirmed MRD negative status. Confirmed MRD negativity was achieved in 11 of 14 subjects, rate 79% (95% exact binomial CI: 49% - 95%). The sample size assumption was confirmed, and enrollment continued as planned (section 1.4).

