## 2. GENERAL ANALYSIS CONSIDERATION

### 2.1. Analysis Sets

**All treated population** includes all enrolled subjects who received at least 1 dose of study drug (ibrutinib or venetoclax or both). All analysis including baseline, disposition, efficacy and safety analysis will be based on this population.

**MRD-negative randomized population:** defined as all treated subjects in the MRD Cohort who are randomized to the double blind ibrutinib or placebo arms. Subjects in this population will be analyzed according to the treatment to which they are randomized.

**MRD-positive randomized population:** defined as all treated subjects in the MRD Cohort who are randomized to the open label ibrutinib or Ibr + Ven arms. Subjects in this population will be analyzed according to the treatment to which they are randomized.

**Non-del 17p population** includes subjects of all treated population without del 17p abnormality according to non-missing baseline FISH results. The primary analysis of the primary and main secondary endpoints for FD cohort will be based on this population.

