**Table 1: Baseline Subgroups**

Baseline Characteristics	Subgroups	Analysis Type
Age	<65 years, ≥65 years	• CRR
Gender	Male, Female	• MRD negativity rate
Race	White, Non-White	• Adverse Event
ECOG score	0, 1-2	• CRR • MRD negativity rate
Rai stage	Stage 0-II, III-IV	
Bulky disease	LDi <5 cm, ≥5 cm	
Del 17p	Yes, No	
Del 17p or TP53 mutated	Yes, No	
FISH*	Del 17p, Del 11q, Others	
IGHV per central lab	unmutated, mutated	
Creatinine clearance	<60 mL/min, ≥60 mL/min	• Adverse Event
NCI ODWG Liver Function Classification	Normal, Abnormal	

ECOG = Eastern Cooperative Oncology Group, FISH = Fluorescence in Situ Hybridization,  
NCI ODWG= National Cancer Institute Organ Dysfunction Working Group

\*Classified in 3 categories per hierarchical order (Dohner et al,2000): del 17p, del 11q without del 17p, and all others (neither del 17p nor del 11q identified).

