Complete response rate (CRR)	The proportion of subjects achieving a best overall response of CR or CRi on or prior to initiation of subsequent antineoplastic therapy or, if applicable, reintroduction of study treatment, whichever occurs earlier.	
Primary The point estimate of CRR per investigator assessment and the corresponding 95% CI based on normal approximation to the binomial distribution will be provided. In FD cohort non-del17p population, p value for testing <math>CRR \leq 37\%</math> vs <math>CRR > 37\%</math> using asymptotic test for the binomial proportion will be calculated.
 
Sensitivity CRR per IRC assessment.
 
Supportive 1. Duration of complete response (DOCR defined as the interval between the date of initial CR or CRi until disease progression or death from any cause, whichever occurs first.) for subjects who achieved CR or CRi. 2. Durable CRR (defined as proportion of subjects with DOCR <math>\geq</math> 336 days (12 cycles))
 
Subgroup (defined in table 1) The point estimate of CRR per investigator assessment and its 95% CI by normal approximation to the binomial distribution for each subgroup.

Secondary Endpoints for MRD and FD Cohorts		
Overall response rate (ORR)	The proportion of subjects achieving a best overall response of CR, CRi, nPR, or PR on or prior to initiation of subsequent antineoplastic therapy or, if applicable, reintroduction of study treatment, whichever occurs earlier.	
Primary The point estimate of ORR per investigator assessment and the corresponding 95% CI based on normal approximation to the binomial distribution will be provided.
 
Sensitivity ORR per IRC assessment.

Duration of response (DOR)	Duration of response will be calculated for the subjects achieving a response (CR, CRi, nPR, PR) per investigator assessment and is defined as time from the date of initial response including PR with lymphocytosis to the date of disease progression or the date of death from any cause, whichever occurs first. For subjects without documented PD or death, DOR was censored at the date of last adequate disease assessment.	
Primary Kaplan-Meier estimates of median DOR time per investigator assessment and landmark estimates with 2-sided 95% CIs.
 
Sensitivity DOR per IRC assessment

Endpoint	Definition	Analysis Method

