MRD negativity rate	The proportion of subjects achieving MRD negativity which is defined as <1 CLL cell per 10,000 leukocytes (<1 x 10  ) as assessed by flow cytometry of a peripheral blood (PB) or bone marrow (BM) aspirate sample per central laboratory on or prior to initiation of subsequent antineoplastic therapy or, if applicable, reintroduction of study treatment, whichever occurs earlier.	
Primary The point estimate of MRD negativity rate and the corresponding 95% CI based on normal approximation to the binomial distribution will be provided.
 
Sensitivity MRD negativity rate by sample type (PB or BM)
 
Supportive MRD negativity rate by best overall response categories (CR/CRi, nPR/PR/PRL, and all others including non-responders and those off study without response assessment).

Tumor Lysis Syndrome (TLS) risk reduction	The reduction of the proportion of subjects who are at high risk of TLS after the ibrutinib lead-in compared with baseline.	
Primary The point estimate of the difference in proportions of subjects with high risk of TLS (at baseline - after ibrutinib lead in) and the corresponding 95% CI (adjusting correlation of paired data) will be provided.
 
Supportive Reduction of the proportion of subjects with hospitalization indicated due to tumor lysis Syndrome (TLS) risk (i.e. subjects with high TLS risk and subjects with medium risk of TLS and creatinine clearance <80 mL/min).

Progression Free Survival (PFS)	
Time from the date of first study treatment to the date of disease progression per investigator assessment or date of death from any cause, whichever occurs first, regardless of the use of subsequent antineoplastic therapy prior to documented PD or death.
 
For subjects without documented PD or death, PFS will be censored at the date of last adequate disease assessment. For subjects without adequate disease assessment post-baseline, PFS will be censored on the date of first study treatment.
	PFS distribution will be estimated by Kaplan-Meier method: median PFS and landmark estimates with 2-sided 95% CIs will be provided.

Overall Survival (OS)	Time from the date of first study treatment to the date of death from any cause. For subjects who are not known to have died at the time of the analysis, OS will be censored at the date of last known alive.	Kaplan-Meier estimates of median OS time and landmark estimates with 2-sided 95% CIs.

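### The FD primary test is an unspecified asymptotic test that does not hold one-sided 0.025, and the normal-approximation intervals fail at high rates and in small subgroups

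*SAP*

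**What the plan says.** SAP Section 1.3 (FD Cohort) sets the null at a complete response rate (CRR, meaning CR or CRi) of 37% or less, tested at one-sided 0.025 in subjects without del 17p "using asymptotic test for the binomial proportion". Table 2 names the test in the same way. Neither place gives the variance or mentions a continuity correction. The only sensitivity analysis listed for CRR is the independent review committee's assessment, so no exact test is planned.

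Section 1.4 says that 125 subjects, at an assumed rate of 50%, "will provide 83% power to ensure the rate is > 37% at 1-side alpha 0.025".

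The number of subjects tested is not fixed. Protocol Section 3.1.3 says "Approximately 125 subjects without del17p will be enrolled into this cohort sequentially after the MRD cohort", and SAP Section 2.1 restricts the test set to treated subjects "without del 17p abnormality according to non-missing baseline FISH results".

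For interval estimates of CRR and overall response rate (ORR), Table 2 says "the corresponding 95% CI based on normal approximation to the binomial distribution will be provided". It sets the same method for CRR in each subgroup and for MRD negativity: "The point estimate of MRD negativity rate and the corresponding 95% CI based on normal approximation to the binomial distribution will be provided". The Table 1 subgroups include "Del 17p or TP53 mutated". Table 1 also plans MRD-negativity subgroups, for which Table 2 gives no interval method.

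SAP Section 1.5.1, by contrast, reports exact binomial intervals for the early MRD assessment: 23/30 (58% to 90%) and 11/14 (49% to 95%).

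**The concern.** This is the FD cohort's only hypothesis test, so its decision rule should be unambiguous and should hold its stated level. An asymptotic test of one proportion comes in several versions, which can have different rejection cutoffs. If the version is not named, a borderline result can be declared either way after the data are seen. The test can also disagree with the confidence interval printed beside it.

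The normal-approximation (Wald) interval is known to behave badly near 0% or 100% and with few subjects. Both situations are foreseeable here. Protocol Section 1.4 cites a 100% response rate with this combination in 38 of 38 evaluable relapsed or refractory subjects, and in all 20 high-risk treatment-naive subjects of a second study. Protocol Section 1.1.1 puts del17p or TP53 abnormalities at 7-10% of cases at diagnosis, which makes that subgroup small.

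**Working it through.** **Inputs.** n = 125, p0 = 0.37, p1 = 0.50, one-sided alpha 0.025 (SAP Sections 1.3 and 1.4), with z = 1.960.

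**The plan's power.** With the variance at p1: Φ[(0.50 − 0.37)·√125 / √(0.50·0.50) − 1.960] = Φ(2.907 − 1.960) = 0.828, which reproduces the stated 83%. With the null variance in the critical value: Φ[(0.13·√125 − 1.960·√(0.37·0.63)) / 0.5] = 0.845.

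**Cutoff and exact size at n = 125.** The test statistic is z = (x/n − p0)/SE. SE is √(0.37·0.63/125) = 0.0432 under the null variance, or √(p̂(1 − p̂)/125) under the sample variance. Exact size is P(X ≥ cutoff) for a binomial with n = 125 and p = 0.37; exact power uses p = 0.50.

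- At 57/125 (45.6%): null-variance z = 0.086/0.0432 = 1.99, so it rejects. Sample-variance z = 0.086/0.0445 = 1.93, so it does not.
- At 58/125 (46.4%): both reject (2.18 and 2.11).

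| Test at n = 125 | Rejects from | Exact size | Exact power |
|---|---|---|---|
| Null variance, uncorrected | 57 | 0.0299 | 0.858 |
| Sample variance, uncorrected | 58 | 0.0196 | 0.814 |
| Null variance, continuity-corrected | 58 | 0.0196 | 0.814 |
| Exact binomial | 58 | 0.0196 | 0.814 |

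The Wald interval at 57/125 is 0.456 ± 1.960·0.0445, or 36.9% to 54.3%. It includes 37% while the null-variance test rejects 37%. The probability of exactly 57 responders at a true 50% is 0.8585 − 0.8144 = 0.044.

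**Other sample sizes.** The same calculation was made for each N from 115 to 135 (21 values; this range is an assumption).

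| Test | N with size above 0.025 | Largest size |
|---|---|---|
| Null variance, uncorrected | 13 of 21 | 0.0315 (N = 118) |
| Sample variance, uncorrected | 6 of 21 | 0.0278 (N = 127) |
| Null variance, continuity-corrected | 2 of 21 | 0.0258 (N = 129) |
| Exact binomial | 0 of 21 | 0.0245 (smallest 0.0163) |

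The largest excess is 0.0315 − 0.025 = 0.0065. A fourth version, sample variance with a continuity correction of 0.5/n, stays below 0.025 throughout this range (largest size 0.0223). It does so by being more conservative than the exact test, and nothing guarantees its level.

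**Intervals.** Wald: p̂ ± 1.960·√(p̂(1 − p̂)/n). Clopper-Pearson limits: the 0.025 quantile of Beta(x, n − x + 1) and the 0.975 quantile of Beta(x + 1, n − x).

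| Result | Wald | Clopper-Pearson |
|---|---|---|
| 122/125 | 94.9% to 100.3% | 93.1% to 99.5% |
| 125/125 | 100% to 100% | 97.1% to 100% |
| 11/14 | 57.1% to 100.1% | 49.2% to 95.3% |
| 57/125 | 36.9% to 54.3% | 36.7% to 54.7% |
| 58/125 | 37.7% to 55.1% | 37.4% to 55.5% |

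The exact interval for 11/14 matches the one in SAP Section 1.5.1. The last two rows show that the exact interval agrees with the exact test on either side of the cutoff.

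**Coverage.** For a true rate p, coverage is the sum of the binomial probabilities of every x whose interval contains p.

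| n | True rate | Wald | Clopper-Pearson |
|---|---|---|---|
| 125 | 0.50 | 95.1% | 95.1% |
| 125 | 0.77 | 94.2% | 95.7% |
| 125 | 0.95 | 94.2% | 96.5% |
| 125 | 0.97 | 88.7% | 96.4% |
| 11 to 15 | 0.50 | 85% to 94% | 96% to 99% |
| 11 to 15 | 0.79 | 81% to 94% | 98% to 99% |

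The subgroup size is 7-10% of the 150 MRD-cohort subjects, or 10.5 to 15, assuming the trial has the same share as at diagnosis. The rates 0.50 and 0.79 are assumptions taken from the SAP's planning value for CRR and from 11/14.

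**The case against.** The SAP's figures lean towards one reading. The stated 83% fits the variance-at-p1 formula (0.828) better than the null-variance formula (0.845), and the planned interval uses the sample variance. On that reading the cutoff at 125 is 58 and the size is 0.0196, identical to the exact test. Even otherwise, only one outcome at 125 changes hands. Approximate size is inherent in any asymptotic test, and this is a single-arm Phase 2 comparison with a historical rate. Naming the variance could be seen as enough.

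On intervals, overall CRR near 50% and MRD negativity near 77% are adequately covered at 125. ORR and the subgroups are descriptive. The 38/38 result comes from evaluable relapsed or refractory subjects, whereas here subjects without a post-baseline assessment count as non-responders and the SAP's ORR leaves out PR with lymphocytosis. SAP Section 4 also limits subgroup output to analyses that are informative. Wilson intervals would be a reasonable alternative, since Clopper-Pearson is conservative.

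Much of this stands as to size: the consequence for the test is small, and the main CRR interval is sound. It does not remove the point. The sample-variance reading is an inference that the SAP does not state, and that version still exceeds 0.025 at 6 of the 21 sample sizes. ORR is a full-cohort secondary endpoint, so the limit on subgroup output does not help it. The SAP gives no reason for abandoning the exact intervals it used in Section 1.5.1.

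**Conclusion.** The concern holds. As written, the FD primary test has no single decision rule and no guaranteed level. At 125 subjects its exact size is 0.0299 or 0.0196 depending on an unstated option, and the result at 57/125 turns on that option. The excess over 0.025 is at most about 0.65 percentage points within the assumed range of 115 to 135 subjects, and exactly 57/125 has a probability of 4.4% at a true rate of 50%.

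The planned intervals can exceed 100%, collapse to zero width or fall well short of 95% coverage for ORR near 100% and for subgroups of about 11 to 15. This rests on the response rates cited in the protocol and on the 7-10% share carrying over to this trial. The overall CRR interval is adequate near the planned rate, and neither the sample size nor the 83% figure, as a normal approximation, is wrong. The matter is modest in size but should be corrected, because it concerns the cohort's only test and the correction is cheap.

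**What to change.** - In SAP Section 1.3 and Table 2, replace the asymptotic test with the exact binomial test for FD CRR. At 125 subjects it rejects at 58 or more responders, with size 0.0196; at any other N the cutoff follows from the same rule.
- In Table 2, specify Clopper-Pearson 95% intervals for CRR, CRR subgroups, ORR and MRD negativity, as Section 1.5.1 already does. Name the same method for the MRD-negativity subgroups in Table 1.
- In Section 1.4, state the power as 81% for 125 subjects, so that it describes the test to be used.

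The cost is SAP wording and one software option. No patients are added and power stays above 80%. The downside is slight conservatism: somewhat wider intervals, and stated power of 81% instead of 83%.

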7.2.3.5. PR with Lymphocytosis (PRL)

Subjects achieve all PR criteria with the exception of lymphocyte criteria.

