10.4.3. Overall Response Rate (ORR)

Overall response rate (ORR) is defined as the proportion of subjects who achieve a CR, CRi, nPR, PR, or PRL as evaluated by investigator using IWCLL 2008 criteria. Subjects who do not have any post-baseline response assessment will be considered as non-responders. It is a secondary endpoint for the MRD cohort and the Fixed Duration cohort. [REDACTED] as exploratory endpoints. A pooled analysis in combination with another dataset (eg, CLL3011; GLOW) may be performed for ibrutinib retreatment. Details of the statistical analysis will be described in a separate SAP as applicable.

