## **6. CHANGES IN PROTOCOL PLANNED ANALYSIS**

- The term “MRD-negative response” was replaced by the phrase “MRD negativity”.

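### ORR counts PR with lymphocytosis (PRL) as a response in the protocol but not in the SAP, and the SAP's list of changes does not record the difference

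*SAP*

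**What the plan says.** Protocol 10.4.3 defines ORR as "the proportion of subjects who achieve a CR, CRi, nPR, PR, or PRL as evaluated by investigator using IWCLL 2008 criteria", and adds: "It is a secondary endpoint for the MRD cohort and the Fixed Duration cohort". SAP Table 2 defines the same endpoint by a "best overall response of CR, CRi, nPR, or PR", reached before subsequent therapy or reintroduction of study treatment. The main SAP analysis uses investigator assessment; a sensitivity analysis by the IRC sits under the same definition.

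Protocol 7.2.2 lists PRL beside PR as a separate response category, and 7.2.3.5 defines it: "Subjects achieve all PR criteria with the exception of lymphocyte criteria".

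Elsewhere in SAP Table 2, the supportive analysis of MRD negativity by best overall response puts CR/CRi in one group, followed by "nPR/PR/PRL, and all others including non-responders" and those off study without a response assessment.

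SAP section 6, on changes to the protocol's planned analysis, has a single entry, under which one MRD term "was replaced by the phrase" for another. It says nothing about ORR or PRL.

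For duration of response (DOR), Protocol 10.4.5 and SAP Table 2 agree. Both take responders to be subjects with CR, CRi, nPR or PR, and both let the clock start at an initial response that may be PRL.

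**The concern.** A named secondary endpoint has two definitions, and the section of the SAP where a reader would look for an explanation is silent. Following the SAP as written gives an ORR that is not the protocol's endpoint. While the choice stays open, the definition could also be settled after the data are seen.

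PRL is a plausible category in this trial. Protocol 1.2.4.8 reports lymphocytosis in 66% of CLL/SLL subjects on ibrutinib, resolving at a median of 14 weeks. The single-agent lead-in lasts 3 x 28 = 84 days, or 12 weeks, and response is first assessed just before Cycle 4. Some subjects may therefore be in PRL at that assessment, and one who stops before the response deepens could keep PRL as best response.

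Within the SAP, the MRD-by-response table places PRL with nPR and PR, apart from the group that contains non-responders. That sits uneasily with an ORR definition under which the same subject is not a responder.

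**Working it through.** The documents state no expected rate, power or alpha for ORR, so there is no planned figure to reproduce. The check is a comparison of definitions, then the arithmetic of one subject's weight.

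**Step 1. Treatment of PRL, place by place**

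| Place | Categories counted or grouped | PRL-only subject |
|---|---|---|
| Protocol 10.4.3, ORR | CR, CRi, nPR, PR, PRL | responder |
| SAP Table 2, ORR | CR, CRi, nPR, PR | not a responder |
| SAP Table 2, MRD by best response | CR/CRi; nPR/PR/PRL; all others | grouped with nPR/PR |
| Protocol 10.4.5, DOR | CR, CRi, nPR, PR | not in the analysis |
| SAP Table 2, DOR | CR, CRi, nPR, PR | not in the analysis |

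Here, PRL-only means that PRL is the subject's best overall response.

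**Step 2. Could PR in the SAP be read as covering PRL?** No. Protocol 7.2.2 and 7.2.3.5 make PRL a separate category. The SAP gives it its own abbreviation and names it beside PR in the MRD grouping. Rows 1 and 2 are a real difference.

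**Step 3. Does the protocol's deferral to the SAP explain it?** Protocol sections 10 and 10.4 leave analysis details to the SAP. But 10.4.3 states the responder set itself, so narrowing it is a change, and section 6 is where changes belong.

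**Step 4. Is DOR in conflict?** Rows 4 and 5 agree. The mention of PRL in the DOR wording fixes only the start date for subjects who also reach PR or better; it does not bring PRL-only subjects into the analysis.

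**Step 5. Size**

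Inputs: N = 125 (Fixed Duration cohort without del17p) and N = 150 (MRD cohort), the planned numbers in Protocol 3.1 and SAP 1.4. Let k be the number of PRL-only subjects. The documents give no value for k; those below are assumed.

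Gap = ORR (protocol) - ORR (SAP) = 100 x k / N percentage points.

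| k (assumed) | N = 125 | N = 150 |
|---|---|---|
| 0 | 0 | 0 |
| 1 | 100 x 1/125 = 0.8 | 100 x 1/150 = 0.67 |
| 2 | 1.6 | 1.33 |
| 5 | 4.0 | 3.33 |
| 10 | 8.0 | 6.67 |

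The gap is never negative, because the SAP's responder set is the protocol's set with one category removed.

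**The case against.** The best defence is that the mismatch hardly matters. SAP 1.6 confines hypothesis testing to the primary endpoints, and neither 1-year DFS nor the CR/CRi rate uses PRL. The SAP definition is the stricter one and cannot flatter the regimen. The PRL-only group may be very small: best response is taken over a period that includes 12 cycles of combination treatment, and a study of the combination in relapsed/refractory CLL cited in Protocol 1.4 reports median blood CLL burden falling from 54.5 to 0.001 x 10^9/L by 8 months. Protocol 7.2.2 also requires a response to last 2 months to be confirmed, so some subjects who stop early may have no confirmed PRL at all. All of this stands. It limits the consequence but does not reconcile the two definitions or account for the silence of section 6.

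The protocol is also not uniform: it counts PRL in ORR and leaves it out of the DOR responder set. The SAP's ORR matches the latter. That may suggest a motive for the narrower definition, but the SAP does not offer it as a reason.

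The MRD-by-response table is a supportive cross-tabulation and never labels the nPR/PR/PRL group as responders. What it shows is a tension in labelling; it does not create another ORR.

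A reader might infer that DOR is inconsistent as well, since its clock can start at PRL. The documents do not support this: the responder set is the same in both, and it matches the SAP's own ORR set.

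**Conclusion.** The point holds as a conflict of definition between Protocol 10.4.3 and SAP Table 2 that section 6 does not disclose. The textual finding is firm; its numerical effect is unknown. It is 0.8 points of ORR per PRL-only subject at N = 125 and 0.67 at N = 150, assuming the planned numbers are the denominators, and zero if no subject has PRL as best response. The direction is fixed: the SAP's ORR equals the protocol's or is lower.

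Two stronger readings should be resisted. One is that ORR will shift by some particular amount, such as a few points; any such figure rests on an assumed PRL rate. The other is that the trial's conclusions are at risk; ORR is descriptive and neither primary endpoint depends on PRL. The correction is worth making because it is cheap and brings the reported secondary endpoint back to the protocol's.

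**What to change.** In SAP Table 2, report ORR by the protocol's definition, with PRL, and add a row for ORR without PRL. Do this for both the investigator and the IRC assessment.

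If the sponsor prefers the narrower definition as the main one, list the removal of PRL in SAP section 6 with a reason and keep both rows.

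Leave the DOR responder set as Protocol 10.4.5 has it. Adding PRL-only subjects to DOR for the sake of uniformity would create a new departure from the protocol. A sentence in the SAP saying that PRL-only subjects are not in the DOR analysis would prevent misreading. A short note to the MRD-by-response table, saying how its nPR/PR/PRL group relates to the ORR responders, would remove the remaining tension.

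The cost is a few lines of SAP wording and one added row for each assessor. No new data are needed, and sample size and primary analyses do not change.

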1.2.4.8. Lymphocytosis

Upon initiation of treatment, a reversible increase in lymphocyte counts (ie, $\geq 50\%$ increase from baseline and an absolute count $>5000/\mu\text{L}$), often associated with reduction of lymphadenopathy, has been observed in 66% of subjects with CLL/ small lymphocytic lymphoma (SLL) treated with ibrutinib. This observed lymphocytosis is a pharmacodynamic effect and should not be considered progressive disease in the absence of other clinical findings ([Hallek 2008](#), [Hallek 2012](#), [Hallek 2013](#)). The onset of isolated lymphocytosis occurs during the first month of ibrutinib therapy and resolves by a median of 14 weeks (range, 0.1 to 104 weeks). When ibrutinib was administered with chemoimmunotherapy (bendamustine + rituximab [BR]), lymphocytosis was 7% with ibrutinib + BR versus 6% with placebo + BR.

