10.4.5. Duration of Response (DOR)

Duration of response will be calculated for subjects achieving a response (CR, CRi, nPR, PR) based on IWCLL response criteria and defined as the interval between the date of initial documentation of a response including PR with lymphocytosis, until disease progression or death from any cause, whichever occurs first. Kaplan-Meier methodology will be used to estimate event-free curves, median, and landmark estimates.

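### Duration of response is limited to subjects who reach PR or better but is timed from the first PR with lymphocytosis (PRL), which gives PRL-first responders a modest stretch of guaranteed event-free time

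*SAP*

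**What the plan says.** The DOR row of SAP Table 2 sets the population first: "Duration of response will be calculated for the subjects achieving a response (CR, CRi, nPR, PR) per investigator assessment". It then sets the clock: "time from the date of initial response including PR with lymphocytosis to the date of disease progression" or death. Protocol 10.4.5 is built the same way, with the same four qualifying categories and a start at the "date of initial documentation of a response including PR with lymphocytosis, until disease progression or death from any cause".

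PRL is a category of its own. Protocol 7.2.3.5 defines it thus: "Subjects achieve all PR criteria with the exception of lymphocyte criteria". It appears in the clock start but not in the list of qualifying responses.

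The planned estimator is "Kaplan-Meier estimates of median DOR time per investigator assessment and landmark estimates with 2-sided 95% CIs". The only DOR sensitivity analysis listed repeats it with the independent review committee (IRC) assessment.

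The documents disagree on whether PRL is a response. SAP Table 2 defines ORR as "The proportion of subjects achieving a best overall response of CR, CRi, nPR, or PR", without PRL. Protocol 10.4.3 counts PRL in ORR. SAP section 6 records only a change of terminology.

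**The concern.** Entry to the DOR set depends on something that happens after the clock has started. If a subject is PRL before Cycle 4 and PR at Cycle 7, the clock runs from the earlier visit, but the subject is in the analysis only because no death or progression intervened. If another subject is PRL before Cycle 4 and fails before reaching PR, that failure appears nowhere in DOR. The first subject contributes guaranteed (immortal) time and the second is removed because of the outcome.

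The visit schedule makes this likely to recur. The first response assessment comes at the end of three 28-day cycles of ibrutinib alone, about week 12. Protocol 1.2.4.8 reports lymphocytosis in 66% of CLL/SLL subjects on ibrutinib and says that it "resolves by a median of 14 weeks". Some subjects will therefore still have it at that visit.

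DOR is a secondary endpoint in both cohorts and the first one listed for the Fixed Duration (FD) cohort. That cohort has a single arm, so no control group shares the effect.

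**Working it through.** The documents give no DOR estimate, target or power, so there is no figure to reproduce. The check has three parts.

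**1. Length of the gap.** Inputs: 28-day cycles (Protocol 3.1.1); response assessment 2-3 days before Cycle 4 (Protocol 8.2.1.3.1 and 8.3.1.3.1); the next assessments at Cycle 7 Day 1 and Cycle 10 Day 1 (Protocol 8.2.1.5, 8.2.1.6, 8.3.1.5 and 8.3.1.6).

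- Cycle 4 to Cycle 7: 3 x 28 = 84 days; 87 days if counted from three days before Cycle 4.
- Cycle 4 to Cycle 10: 6 x 28 = 168 days; 171 days on the same basis.

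**2. Can an event fall in the gap?** Death cannot, because the subject must live to reach PR. Progression is excluded in practice: treatment stops at confirmed progression (Protocol 9.2), and in SAP Table 2 ORR counts responses only up to new therapy or reintroduction. The SAP does not state outright that the qualifying response must precede progression.

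**3. Size.** Let f be the share of the DOR set whose first response is PRL, g the gap in months (days / 30.4375), and S(t) the true event-free curve with constant hazard, lambda = -ln S(24) / 24. Then

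S_SAP(24) = (1 - f) x S(24) + f x exp(-lambda x (24 - g)).

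Worked example with S(24) = 0.80, f = 0.66 and g = 171 days = 5.618 months: lambda = 0.009298, exp(-0.009298 x 18.382) = 0.8429, and 0.34 x 0.80 + 0.66 x 0.8429 = 0.8283, a rise of 2.83 points.

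Rise in 24-month DOR, in percentage points:

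| True 24-month rate | f | g = 87 days | g = 171 days |
|---|---|---|---|
| 90% | 10% | 0.11 | 0.22 |
| 90% | 30% | 0.34 | 0.67 |
| 90% | 66% | 0.75 | 1.48 |
| 80% | 10% | 0.22 | 0.43 |
| 80% | 30% | 0.65 | 1.29 |
| 80% | 66% | 1.42 | 2.83 |

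Over the same grid the median rises by about 0.3 to 3.7 months. The median itself would be 157.9 months at 90% and 74.6 months at 80%.

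A simulation of 2,000,000 subjects with f = 30% and g = 87 days compared three rules. With a true rate of 90%, the SAP rule gave 90.3%; starting at PR gave 90.0%, and so did starting at PRL with PRL-only subjects included. With 80%, the SAP rule gave 80.7% and both matched rules 80.0%. No included PRL-first subject had an event in the gap. The subjects dropped for early failure were 0.37% and 0.80% of the total.

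The two matched rules agree here because the hazard is constant. In real data they estimate slightly different quantities.

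**The case against.** The strongest reply is that the effect is small and DOR is not where the trial's durability claim rests. Most of this stands.

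- SAP 1.6 tests only the primary endpoints, so no alpha, power or sample size is affected. PFS runs from first dose and counts every PRL-only failure. Duration of complete response and durable CRR start at CR or CRi in subjects with CR or CRi, so population and start already match.
- The PRL-first share is unknown. The 66% is a lymphocytosis rate, with onset in the first month, and many cases would have cleared by week 12. Under Protocol 7.2.3.4 a subject whose only baseline abnormalities were nodes, or nodes and lymphocyte count, needs only the nodal criterion for PR, so some subjects with lymphocytosis may already be labelled PR.
- The rise is within sampling error. With 120 responders (assumed) and a rate of 90%, the 95% half-width is 1.96 x sqrt(0.9 x 0.1 / 120), about 5 points.
- At 90% the median of about 13 years lies beyond the roughly 10 years of FD follow-up in Protocol 3.1, so the shift in the median may never be seen.
- Failures between PRL and PR may be rare: the early combination studies in Protocol 1.4 report response in all evaluable subjects. If so, a PRL start that includes PRL-only subjects would land close to the SAP result, and the remaining question is which start date to prefer.
- Starting at PRL is defensible in itself. The protocol treats PRL as an objective response and lymphocytosis as a drug effect rather than treatment failure.

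This limits the size of the effect and rules out insisting on a PR start. It does not remove the mismatch: neither the plain Kaplan-Meier analysis nor the IRC version addresses it.

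On direction, compared with a PR start the shift can only be upward, because included times are lengthened and none is shortened. Compared with a PRL start that includes everyone, it is upward insofar as the subjects left out are early failures; a PRL-only subject who stays event-free would pull the other way.

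**Conclusion.** The point holds in a limited form. The DOR population and clock start do not match in either document, and PRL-first responders gain about 84 days (168 if PR is first recorded at Cycle 10) in which no event can be counted. On the assumptions of constant hazard, a PRL-first share of 10-66% and scheduled visits only, 24-month DOR is raised by 0.1 to 1.5 points at a true 90%, and by 0.2 to 2.8 points at 80%. An unscheduled assessment could shorten the gap.

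A reader might infer something larger. If every responder were PRL-first, a true 24-month rate of 70% would read 72.9% with an 84-day gap or 76.0% with 168 days. The documents do not support that: they give no PRL-first share, and no 70% rate for this regimen. Nor do they support the view that the trial's durability evidence as a whole is biased, since PFS, duration of complete response and durable CRR are untouched.

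The correction is worth making because the effect runs in the regimen's favour and costs almost nothing to remove.

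**What to change.** In the DOR row of SAP Table 2, make population and clock start agree, for both the investigator and the IRC versions. Either rule does this:

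- start at the first CR, CRi, nPR or PR, which fits the SAP's ORR and the way duration of complete response is built; or
- keep the PRL start and add subjects whose only response is PRL, which fits the protocol's ORR.

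Name one as primary and report the other as a sensitivity analysis. Decide in the same edit whether ORR counts PRL, since Protocol 10.4.3 and SAP Table 2 differ, and let that decision guide the choice for DOR. State that a qualifying response must precede progression. Log each departure from the protocol in SAP section 6, and fix the choice before DOR is analysed, because the FD cohort is open-label.

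The cost is SAP wording and one derivation on data already collected. Reported DOR becomes slightly shorter, and one option departs from the protocol's start date while the other departs from its population.
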